### **8.5.3 Exploratory Efficacy Analyses**

VAS for Eyebrows scores will be summarized using percent change from baseline at Week 24. Descriptive statistics will be presented with 90% confidence intervals around the mean (t-distribution). Results will also be listed in the by-patient data listings.

The satisfaction of hair quality questions will be summarized with descriptive statistics at baseline and Week 24, and will be listed in the by-patient data listings. Responses to the patient satisfaction question will be summarized as proportions with 90% confidence intervals. Responses will be also categorized as “Satisfied” (including responses of “Very satisfied,” “Mostly satisfied,” and “Somewhat satisfied”) and “Dissatisfied” (including responses of “Very dissatisfied” and “Dissatisfied”) and presented as a 2 x 2 shift table from baseline to Week 24.

Additional analyses by dosing regimens will be performed at Weeks 4, 8, 12, 16, 20, and 24 for patients who achieve an absolute SALT score of  $\leq 10$ ,  $\leq 20$ , or  $\leq 25$ . Responders by visit will be summarized with proportions and 90% confidence intervals (using the binomial approximation with a Wald continuity correction).

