11.2. Endpoints

11.2.1. Efficacy

The primary efficacy endpoint will be relative change in SALT score for each dose regimen from baseline at Week 24.

Secondary efficacy endpoints in each dose regimen include:

- Proportion of patients achieving at least a 90%, 75%, and 50% reduction in SALT score from baseline at Weeks:
- 4, 8, 12, 16, 20, and 24 in the Treatment Period
- Absolute Change in SALT scores from baseline at Weeks:
 - 4, 8, 12, 16, 20, and 24 in the Treatment Period
- Relative Change in SALT scores from baseline at Weeks:
 - 4, 8, 12, 16, 20 and 24 in the Treatment Period
- Change in satisfaction of hair coverage as reported by the patient

Exploratory endpoints in each dose regimen include:

- Change in patient's eyebrows as measured by the patient's Visual Analog Scale (VAS)
- Change in satisfaction of hair coverage quality as reported by patient

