### **4.1 Efficacy Population**

The Efficacy Population will include all patients who receive study drug and have at least 1 post-treatment SALT assessment during the Treatment Period. Patients in the Efficacy Population will be analyzed according to their randomized dosing regimen.

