## **6. DEMOGRAPHIC AND OTHER BASELINE CHARACTERISTICS**

Demographic characteristics (ie, sex, ethnic origin, race, date of birth, and calculated body mass index) will be collected at the Screening Visit, between Day -28 and -1, and detailed on the eCRF. Demographic characteristics will be summarized using descriptive statistics for all randomized patients.

Baseline characteristics will be summarized using descriptive statistics for all randomized patients and will include the following:

- baseline total SALT score.
- alopecia areata type (current episode; defined below).
- alopecia areata type (at disease onset; defined below).
- duration of current episode in months (calculated as: [date of randomization – date of current episode onset + 1] / 30.4375).
- duration of disease at onset in months (calculated as: [date of randomization – date of disease onset + 1] / 30.4375).
- current nail involvement.
- current eyelash/eyebrow involvement.
- current other facial hair involvement.
- prior Herpes Zoster vaccination.
- time since Herpes Zoster vaccination in months.

Other co-morbidities may be identified and included as baseline characteristics.

The patient's alopecia areata will be classified by the Investigator into one of three categories defined for this study:

- 1) Alopecia areata: patchy type hair loss,
- 2) Alopecia totalis or universalis: complete hair loss on the scalp with or without body hair loss,
- 3) Alopecia ophiasis: band-like hair loss limited to the periphery of the scalp along the back of the hair line in the occipital region and possibly extending over each ear in temporal regions.

The alopecia totalis and alopecia universalis category will be separated into each individual subtype for summaries. Alopecia areata category at baseline, defined as the current episode, and

alopecia areata category at disease onset will be summarized with the number and percent of patients in each category.

All demographics and baseline characteristics will also be listed within a by-patient data listing for all randomized patients.

Medical history will be summarized by frequencies of System Organ Class (SOC) and preferred term and will be coded using MedDRA Version 19.1. All medical history for each patient in the Safety Population will be included in a data listing.

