#### **8.3.1 Visual Analog Scale**

The VAS is a scale of continuous measure initially developed for pain that has been used in a variety of clinical settings where the endpoint of interest is based on a subjective perception. The VAS is a distinct 100 millimeter line anchored on the left end at full degree of impairment and on the right end at no degree of impairment, where indication of the degree of impairment perceived at the time of assessment is captured by marking the appropriate position on the line between the anchor points. The measured distance of the mark from the left anchor will be recorded in millimeters.

As specified in the Schedule of Events, patients will rate his/her eyebrows on the patient VAS. The left and right anchor points for the patient's eyebrow VAS are "None" and "Full", respectively. The patient VAS will measure the patient's eyebrows at the time of completion.

Since the VAS was measured right to left in terms on increasing impairment, the VAS analysis value will be calculated by taking 100 minus the collected value

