## **8.4 Overview of Efficacy Analysis Issues**

### **8.4.1 Handling of Dropouts or Missing Data**

The Last Observation Carried Forward (LOCF) approach will be implemented for missing SALT score data, e.g., if the SALT score in the Week 16 visit window is missing, the next and closest available on-treatment SALT score measurement before the Week 16 visit window will be used for all remaining SALT assessments: Week 16, Week 20 and Week 24. Missing baseline values will not be carried forward. If a SALT assessment is missing between two non-missing SALT

assessments visits, the SALT score at that visit will be interpolated using the mean of the closest pre- and post-assessments.

If the number of discontinuations due to adverse events is substantial, other methods will be explored.

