**Table 8-1 Efficacy Variables and Analysis Methods**

Efficacy Variables	Collection Times	Method
Primary		
SALT (relative change)	Baseline, Week 24	Mean and 90% confidence interval (t-distribution)
Secondary		
Responder Analysis	Baseline, Week 4, 8,	Proportion and 90%
SALT (90%, 75%, 50% relative reduction)	12, 16, 20, 24	confidence interval (binomial approximation)
SALT (absolute change)	Baseline, Week 4, 8, 12, 16, 20, 24	Mean and 90% confidence interval (t-distribution)
SALT (relative change)	Baseline, Week 4, 8, 12, 16, 20, 24	Mean and 90% confidence interval (t-distribution)
Satisfaction of hair coverage	Baseline, Week 24	Proportion and 90% confidence interval (binomial approximation); Shift table
Exploratory		
VAS for Eyebrows (percent change)	Baseline, Week 24	Mean and 90% confidence interval (t-distribution)
Satisfaction of hair coverage quality	Baseline, Week 24	Proportion and 90% confidence interval (binomial approximation); Shift table
SALT ( $\leq 10$ , $\leq 20$ , $\leq 25$ absolute score)	Baseline, Week 4, 8, 12, 16, 20, 24	Proportion and 90% confidence interval (binomial approximation)

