## 14. LIST OF PLANNED TABLES

Table ID	Table No.	Title	Population	Unique?
DS_TAA	14.1.1	Summary of Patient Disposition	All Screened Patients	Y
DS_TAB	14.1.2	Summary of Protocol Deviations	All Randomized Patients	Y
DM_TAA	14.1.3	Summary of Demographics	All Randomized Patients	Y
DM_TAB	14.1.4	Summary of Baseline Characteristics	All Randomized Patients	Y
MH_TAA	14.1.5	Summary of Medical History by System Organ Class and Preferred Term	Safety Population	Y
EX_TAA	14.1.6	Summary of Study Drug Administration and Compliance by Dosing Regimen	Safety Population	Y
CM_TAA	14.1.7.1	Summary of Prior Medications	Safety Population	Y
CM_TAB	14.1.7.2	Summary of Concomitant Medications	Safety Population	N
EF_TAA	14.2.1	Summary of Relative Change from Baseline in Total SALT Score at Week 24	Efficacy Population	Y
EF_TAC	14.2.2.1	Summary of Total SALT Scores by Dosing Regimen and Visit	Efficacy Population	Y
EF_TAE	14.2.2.2	Summary of 90%, 75%, and 50% Responders (SALT Relative Change) by Visit	Efficacy Population	Y
EF_TAG	14.2.2.3	Summary of Satisfaction of Hair Coverage Question	Efficacy Population	Y
EF_TAH	14.2.2.4	Shift from Baseline to Week 24 Satisfaction of Hair Coverage Question	Efficacy Population	Y
EF_TAI	14.2.3.1	Summary of Visual Analog Scale for Eyebrows (mm)	Efficacy Population	Y
EF_TAJ	14.2.3.2	Summary of Satisfaction of Hair Coverage Quality Questions	Efficacy Population	N
EF_TAK	14.2.3.3	Shift from Baseline to Week 24 Satisfaction of Hair Coverage Quality Questions	Efficacy Population	N

EF_TAL	14.2.3.4	Analysis of Patients Achieving $\leq 10$ , $\leq 20$ , or $\leq 25$ Absolute SALT Scores by Visit	Efficacy Population	Y
AE_TAA	14.3.1.1	Summary of Treatment-Emergent Adverse Events	Safety Population	Y
AE_TAB	14.3.1.2	Summary of Treatment-Emergent Adverse Events by System Organ Class and Preferred Term	Safety Population	Y
AE_TAC	14.3.1.3	Summary of Treatment-Emergent Serious Adverse Events by System Organ Class and Preferred Term	Safety Population	N
AE_TAD	14.3.1.4	Summary of All Treatment-Emergent Adverse Events Leading to Discontinuation of Study Drug System Organ Class and Preferred Term	Safety Population	N
AE_TAE	14.3.1.5	Summary of Treatment-Emergent Adverse Events Resulting in Study Dose Interruption by System Organ Class and Preferred Term	Safety Population	N
AE_TAF	14.3.1.6	Summary of CTCAE Grade 3-4 Hematology Treatment-Emergent Adverse Events by System Organ Class and Preferred Term	Safety Population	N

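### The eyebrow VAS is to be analysed as mean percent change, with no rule for zero or near-zero baselines; change in mm avoids the problem

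*SAP*

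**What the plan says.** SAP 8.5.3 reads: "VAS for Eyebrows scores will be summarized using percent change from baseline at Week 24". It adds descriptive statistics and a 90% t-interval around the mean. Table 8-1 labels the variable as percent change too. No other change measure for this scale appears in the SAP text.

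The scale is a 100 mm line from no eyebrows (left) to full eyebrows (right), measured from the left. SAP 8.3.1 reverses it before analysis: "the VAS analysis value will be calculated by taking 100 minus the collected value". On the analysis scale, 0 is full eyebrows and 100 is none.

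Four other places bear on the point:

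- Protocol 11.2.1 and SAP 8.3 define the endpoint as change, without naming a percent scale. Planned Table 14.2.3.1 carries mm in its title.
- SAP 4.1 sets no eyebrow condition: "The Efficacy Population will include all patients who receive study drug and have at least 1 post-treatment SALT assessment during the Treatment Period". Nor do the inclusion criteria in Protocol 7.1.
- SAP 6 lists "current eyelash/eyebrow involvement" among the baseline characteristics, so involvement is expected to vary between patients.
- The missing-data rule in SAP 8.4.1 is confined to SALT: the last-observation "approach will be implemented for missing SALT score data".

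**The concern.** Percent change divides by the baseline value. Here the baseline is the eyebrow deficit, and nothing in the design keeps it away from zero. A patient who marks the full end of the line on Day 1 has a zero denominator and no value. A patient a few mm short of full has a tiny denominator, so a small worsening becomes several hundred percent. One such patient can dominate the mean and standard deviation of an arm of about 25.

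This is foreseeable. Totalis and universalis together are limited to about 75% of enrolment, so patchy and ophiasis patients are expected. Protocol 9.1 also defines the totalis/universalis category as complete scalp loss with or without body hair loss.

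SALT does not share the problem. Entry requires a score of at least 50, so the worst possible relative worsening is 100 × (100 - 50)/50 = 100%. Yet SALT is given both absolute and relative change, while the VAS, which has no such floor, is given only the relative form.

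At stake is whether the eyebrow result can be read at all. There is also the prospect of choosing how to handle these patients after the data have been seen.

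**Working it through.** The documents give no VAS mean, SD or share of patients near full eyebrows, so there is no plan figure to reproduce. What follows is an illustration.

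**Inputs from the documents.** 25 completers per arm (SAP 2.6), 90% intervals (SAP 3), analysis value = 100 minus the mark (SAP 8.3.1).

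**Assumptions.** Typical patients go from 80 to 48 mm. That is -40% with an assumed SD of 30 points, or -32 mm with an assumed SD of 24 mm (30% of 80). Change is Week 24 minus baseline, so negative means improvement.

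**Step 1: no affected patient.** Half-width = t(0.95, 24) × SD/√25 with t = 1.711.

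- Percent: 1.711 × 30/5 = 10.3 points.
- mm: 1.711 × 24/5 = 8.2 mm.

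**Step 2: one of the 25 patients has a low baseline.** Let v be that patient's percent change and d the change in mm. The other 24 keep the assumed mean and SD.

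- Percent: mean = (24 × (-40) + v)/25; SD² = [23 × 30² + (24/25)(v + 40)²]/24.
- mm: mean = (24 × (-32) + d)/25; SD² = [23 × 24² + (24/25)(d + 32)²]/24.

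| One patient goes from → to (mm) | v | Mean %, half-width | Mean mm, half-width |
|---|---|---|---|
| none affected | – | -40.0, 10.3 | -32.0, 8.2 |
| 20 → 30 | +50% | -36.4, 11.8 | -30.3, 8.5 |
| 10 → 20 | +100% | -34.4, 13.9 | -30.3, 8.5 |
| 5 → 15 | +200% | -30.4, 19.3 | -30.3, 8.5 |
| 2 → 10 (stress case) | +400% | -22.4, 31.7 | -30.4, 8.5 |
| 2 → 0 | -100% | -42.4, 10.9 | -30.8, 8.3 |
| near full, unchanged | 0% | -38.4, 10.4 | -30.7, 8.3 |

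For example, 5 → 15 gives SD² = [20,700 + 0.96 × 240²]/24 = 3,166.5, so SD = 56.3 and half-width = 1.711 × 56.3/5 = 19.3.

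**Step 3: effect on the regimen difference.** The comparison is with an unaffected arm (mean -40, SD 30, n = 25), using Welch 90% intervals in percentage points.

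- No stress-case patient: 0 (-14.2 to 14.2).
- One (mean -22.4, SD 92.8): 17.6 (-15.5 to 50.7).
- Two (mean (23 × (-40) + 2 × 400)/25 = -4.8, SD 125.2): 35.2 (-8.7 to 79.1).

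All three intervals include zero. The damage is lost information, not a spurious difference.

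**Step 4: baselines of exactly 0.** If these patients are dropped, the half-width is t(0.95, n - 1) × 30/√n. It is 10.5, 10.7 and 11.0 points for n = 24, 23 and 22, against 10.3 for 25. That loss is small.

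**The case against.** The strongest reply has five parts.

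- **The shells may already show mm.** Table specifications sit in a separate attachment, and the title of Table 14.2.3.1 is in mm, so observed mm values may well be tabulated. This stands as a reservation. The shells are not available here, and the SAP text itself specifies no absolute change.
- **Other planned output softens the problem.** SAP 3 adds the median, range and n, SAP 8.6 adds summaries by subtype, and a by-patient VAS listing is planned. These would expose an extreme value, and the median resists it. They do not repair the specified mean and interval, a median cannot include an undefined value, and subtype does not fix eyebrow status.
- **The example leans on worsening.** Both arms receive active drug, and a near-full patient who improves or stays the same barely moves the result, as the last two table rows show. This is fair, and no document figure says how often worsening would occur. The 5 → 15 mm row shows, however, that the instability does not need the stress case.
- **Percent change is a legitimate reading of the protocol.** It parallels the primary SALT measure, and the protocol leaves the detail to the SAP. This also stands: no passage is contradicted. The complaint is that the measure chosen has no rule for a baseline the design permits.
- **Change in mm has its own cost.** Patients with no eyebrow loss dilute the mean. This is true, and the cost is set out with the fix.

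**Conclusion.** The concern holds, as a minor point. Followed as written, the SAP gives no value for a patient with full eyebrows at baseline, and it can give an unstable mean and interval when a patient starts close to full. Under the assumptions above, one patient in 25 worsening by 10 mm raises the percent half-width from 10.3 to between 11.8 and 19.3 points, depending on the baseline. The mm half-width rises only from 8.2 to 8.5. The stress case reaches 31.7 points, but nothing in the documents supports a frequency for it.

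These sizes depend on assumed VAS means and SDs, and the number of affected patients is unknown. Losing the zero-baseline patients costs little precision; the near-zero baselines and the missing rule matter more. The endpoint is exploratory, no hypothesis test is planned, and the primary SALT analysis is not affected.

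**What to change.** In SAP 8.5.3, replace the sentence with wording such as:

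> *Eyebrow VAS will be summarised as absolute change in mm from baseline to Week 24 in Efficacy Population patients with both assessments, with a 90% t-interval for the mean in each dosing regimen and for the difference between regimens.*

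The interval for the difference is included because Protocol 11.4.2 plans one for continuous measures at Week 24. In Table 8-1, change the label from percent change to absolute change in mm. Change in mm is defined for every patient with both readings, is bounded by -100 and +100, and fits both the protocol's endpoint and the unit in the Table 14.2.3.1 title.

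If percent change is kept, state what happens at baseline 0, set a minimum baseline, and report how many patients fall below it.

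The cost is SAP wording and possibly one table shell, with no new data. There are two downsides. The result is no longer on the same relative scale as SALT, and uninvolved patients pull the mean towards zero. In the same example, if 5 or 10 of 25 patients are uninvolved and unchanged:

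- All patients: 20 × (-32)/25 = -25.6 mm (half-width 8.6), or 15 × (-32)/25 = -19.2 mm (half-width 8.3).
- Involved patients only: -32.0 mm, with half-width 9.3 (n = 20) or 10.9 (n = 15).

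A supporting summary in patients with baseline eyelash or eyebrow involvement would show the undiluted change. That item combines lashes and brows, so it would also include patients with lash loss only.

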## **8.6 Examination of Subgroups**

Descriptive statistics will be provided by alopecia subtype.

## **9. SAFETY EVALUATION**

### **9.1 Overview of Safety Analysis Methods**

Safety and tolerability of CTP-543 will be assessed by evaluating the following for the Safety Population:

- Adverse events
- Clinical laboratory results
- Vital signs
- Electrocardiogram (ECG) results
- Concomitant medications
- Physical examinations

All safety summaries will be descriptive with no statistical hypothesis testing and based on the Safety Population. Patients will be summarized according to the study drug received (i.e., as treated), should it differ from the randomized dosing regimen. All safety endpoints will be listed in by-patient data listings.

### **9.2 Adverse Events**

Adverse events will be coded using MedDRA and summarized by system organ class and preferred term. Clinically significant deteriorations in physical examination findings will be reported and summarized as adverse events.

An adverse event reported after informed consent, but before the first dose of study drug (i.e., Day 1), will be considered a pre-treatment adverse event. Treatment-emergent adverse events will be defined as any adverse event that occurs after administration of the first dose of study drug. The number and percentage of patients who report TEAEs will be summarized by system organ class and preferred term.

Treatment emergent adverse events will also be summarized by intensity as well as relationship to study drug.

Partial dates will be imputed for the purposes of defining TEAEs as follows:

- For a missing start day where the month and year are present, the start day will be set to the first day of the month, unless 1) the first day of the month is before the date of administration of study drug and the month and year are the same as the month and year of the date of administration of study drug, and 2) the end date is on or after the date of

administration of study drug or the end date is completely missing, in which case the start day will be set to the first day of administration of study drug.

- For a missing start day and month where the year is present, the start day and month will be set to January 1st, unless 1) January 1st is before the date of administration of study drug, and 2) the end date is on or after the date of administration of study drug or the end date is completely missing, in which case the start day and month will be set to that of the first date of administration of study drug.
- For a missing end day where the month and year are present, the end day will be set to the last day of the month, unless the month and year are the same as the month and year of the last contact date for the patient, in which case the end day will be set to that of the patient's last contact date.
- For a missing end day and month where the year is present, the end day and month will be set to the patient's last contact date, unless the year of the patient's last contact date is greater than the end year, in which case the end day and month will be set to December 31st.

For an entirely missing stop date (i.e. day, month, and year are missing), the TEAE will be treated as ongoing.

Patients who report the same preferred term on multiple occasions will be counted once for the preferred term: under the highest severity when summarized by severity and under the closest relationship to study drug when summarized by relationship. Missing severity or relationship will not be imputed. If a patient reports multiple preferred terms for a SOC, the patient will be counted only once for that SOC.

The number and percentage of patients who experience TEAEs will be summarized by dosing regimen for the following:

- By SOC and preferred term.
- By severity/intensity, SOC, and preferred term.
- By relationship to study drug, SOC, and preferred term.
- Serious adverse events (SAEs) by SOC and preferred term.
- SAEs by relationship to study drug, SOC and preferred term.
- AEs resulting in discontinuation of study drug by SOC and preferred term.
- AEs that result in study drug dose interruption by SOC and preferred term.
- AEs that meet Grade 3-4 Common terminology criteria for adverse events (CTCAE) hematology results by system organ class and preferred term.

- AEs that meet Grade 3-4 CTCAE serum chemistry results by system organ class and preferred term.

By-patient listings will be provided for all AEs, SAEs, and AEs related to the study drug, as well as AEs leading to study drug withdrawal or death. A by-patient listing will also be created for any pregnancies that occur. TEAEs that result in dose interruption will also be identified.

